5. Data handling	5
5.1 Missing data.....	5
6. Statistical Analysis	6
Sensitivity analysis	11
Fall outcomes	11
Fall-related risk factor outcomes	11
6.3. Major Protocol Deviations	11
7. Implementation of Analysis Plan	11
STATA CODE.....	11
8. References	13

1. Study Synopsis

Falls are common among older adults and can have severe consequences such as disability, decreased quality of life, and premature death [1–4]. Perturbation-based balance training (PBT) has recently gained interest as a potential brief, effective, and sustainable fall preventive strategy [5]. During PBT, participants are exposed to repeated slips and trips during walking while wearing a safety harness in a laboratory. Two meta-analyses, looking at eight and four PBT studies, have shown a vaccination-like effect of almost 50% decreased fall rates after even small dosages (1–8 sessions) [6–8]. Nonetheless, more evidence is needed to evaluate the effects of PBT performed on a treadmill [8]. This assessor-blinded, parallel-group, randomised, controlled trial will evaluate the effects of treadmill-PBT on falls and other relevant physical, cognitive and sociopsychological factors among community-dwelling older adults.

2. Study Objectives, Hypothesis, and Outcomes

2.1. Primary Objective and Outcome (if applicable)

The primary objective of this study is to determine the effects of a four-session PBT intervention on fall rates (number of falls per person-year) in community-dwelling older adults aged 65 or older compared to treadmill walking without perturbations.

The main hypothesis is that treadmill-PBT will decrease the fall rate by up to 50% in the 12 months following the intervention compared to time-matched treadmill walking.

2.2. Secondary Objectives and Outcomes

The secondary objectives are to evaluate the effects on additional fall metrics and the potential transfer effects of PBT to other relevant physical, cognitive, and social-psychological risk factors.

The secondary fall metrics include the proportion of fallers, the time to first fall, the proportion with at least one fall-related fracture, the rate of fall-related fractures, the proportion with at least one fall-related injury, the rate of fall-related injury, the proportion with at least one fall-related health-care contact, and the rate of fall-related health-care contact. It is expected that the proportion of fallers is 50% lower in the PBT-group compared to the treadmill walking group.[6,9] However, we do not have enough evidence regarding the remaining fall-related outcomes to make hypothesis hereof; thus, these outcomes are considered exploratory.

The secondary fall-related risk factors included are single- and dual-task gait speed, reaction time, single- and dual-task static balance, lower extremity performance, executive function, health-related quality of life, and fear of falling. These secondary outcomes were chosen as they all have been identified as fall risk markers [10–16]. However, there is insufficient information about such outcomes following PBT; therefore, we consider these outcomes exploratory.

2.3. Descriptive Outcomes

Descriptive data include height, weight, sex, physical and cognitive function, medication usage, Tilburg Frailty Indicator, highest education level, living arrangements, and fall history, including associated injuries, everyday activity functionality (Vulnerable Elders Survey-13), physical activity levels, and home care usage. Information will be collected through a combination of self-reporting, measurements, questionnaires, and medical/municipality records. Descriptive data will be presented in a table stratified by intervention type as mean and standard deviation (normally distributed continuous variables), median and inter-quartile range (not normally dis-

tributed continuous variables), or number and percentage (categorical variables). Descriptive data will be visually compared to evaluate any potential differences between groups.

2.4. Specification of endpoints

2.4.1. Primary Endpoint

The primary endpoint will be the fall rate 12 months after completion of the third training session, and it will be collected using monthly fall calendars as recommended.[17]

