2.4.2. Secondary Endpoints

Secondary outcomes and their endpoints are outlined in table 1 and 2. The secondary fall outcomes will be collected using the fall calendars for 12 months. The fall-related risk factor outcomes will be collected at the pre- and post-training test and the 26- and 52-week follow-up.

3. Study Design

This study is designed as an assessor-blinded, randomised, parallel-group (1:1 ratio), controlled trial

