3.2. Randomisation and Blinding

After the pre-training tests, participants will be randomly allocated to either the PBT or treadmill walking group using a permuted block randomisation module in REDCap to ensure similar group sizes (Research Electronic Data Capture; version 9.5.6). Random block sizes (two, four, six, or eight) will ensure that allocation concealment is maintained. The allocation sequence will be generated by a research staff member not involved in enrolling or assigning participants to groups.

4. Study Population

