5.1 Missing data

The number of missing observations and the associated reasons will be reported. For the primary outcome, fall rates, missing data will not be imputed; however, the analysis will be adjusted for follow-up time (days of follow-up will be used as an offset). Likewise, missing data regarding the secondary binary outcomes will neither be imputed, but the modified Poisson regression will be adjusted for person-years (days of follow-up will be used as an offset). For participants who do not return any fall calendars 0 falls and 0 person-years will be registered. However, if more than 10% of data is missing in any outcomes, a sensitivity analysis utilising multiple imputations will be conducted.

Missing data in continuous outcome are expected to be missing at random; thus, they will not be imputed as it has shown that multiple imputations do not add any benefits to a linear mixed-effects model.[25]

6. Statistical Analysis

All statistical tests will be performed using an intention-to-treat approach. Moreover, a per-protocol analysis will also be performed, including only participants who complete 75% or more of the training sessions. The secondary outcome will not be adjusted for multiple comparisons; thus, these results should be considered exploratory.

Count data will be reported as incidence rate ratios (IRR) with 95% confidence intervals (95% CI). Binary outcomes will be reported as risk ratios (RR) and 95% CIs. When appropriate, continuous variables will be reported as either mean and standard deviation or median and interquartile range.

Table 1 Variables, measures, and methods of analysis for fall outcomes.

Primary outcome					
Variable/outcome	Mode of assessing	Time frame	Variable type	Assumption	Methods of analysis
Fall rate (falls per person-year)	Fall calendars	Continuously for 12 months	Count	Equal mean and variance *	Poisson regression Alternative: Bootstrapping [†]
Secondary fall outcomes					
Variable/outcome	Mode of assessing	Time frame	Variable type	Assumption	Methods of analysis
Proportion of fallers	Fall calendars	Continuously for 12 months	Binary	Equal mean and variance *	Poisson regression with robust error variance
Time to first fall	Fall calendars	Continuously for 12 months	Survival	Linear relationship between log hazard and covariate ^a	Cox proportional hazard

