Short Falls Efficacy Scale	7-item questionnaire; score from 7-28 (lower score indicates better performance)	Pre-training test; post-training test; 26- week follow-up; 52-week follow-up	Continuous (ordinal)	Normal distribution of residuals and random effects * [◊] Homogeneity of variance [◊]	Linear mixed-effects model [○]

EuroQoL 5D-5L	
5-item questionnaire and visual analogue scale; index from 0-1 (higher score indicates better performance)
 
Visual analogue scale from 0-100 (higher score indicates better performance)
	
Pre-training test; post-training test; 26-week follow-up; 52-week follow-up
	
Continuous (ordinal)
	
Normal distribution of residuals and random effects^{*†} Homogeneity of variance[‡]
	
Linear mixed-effects model[○]

---------------	---	--	-----------------------------	---	---

* Examined by visual inspection of histograms and QQ-plots; [†] Examined by visually inspecting residuals plotted against fitted values; [‡] If data is not normal-distributed; [‡] Violations of assumptions will be noted; however, no alternative method will be used, as the linear mixed-effects model is robust against such violations; [○] Participant ID as the random effect

Sensitivity analysis

Fall outcomes

For the primary outcome (fall rates) and secondary fall outcomes, a sensitivity analysis adjusting for known confounders (age, sex, and previous falls) will be conducted to evaluate the robustness of the results. Furthermore, if the count variable data is over-dispersed, a poisons regression with bootstrapping will be performed; however, a sensitivity analysis without bootstrapping will also be carried out. These analyses were planned before the commencement of data collection. Additional fall rate sensitivity analyses 1) only including participants with no prior history of falls 12 months before study commencement and 2) only including participants with a history of falls 12 months before study commencement will also be conducted. These sensitivity analyses were planned after data collection began.

Fall-related risk factor outcomes

Before data collection commenced, it was determined to conduct a sensitivity analysis on the secondary fall-related risk factors adjusting for age, sex, and previous falls will be carried out.

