6.3. Major Protocol Deviations

Major protocol deviations will be reported in the trial registration at ClinicalTrials.gov ([NCT04733222](https://clinicaltrials.gov/ct2/show/NCT04733222)), the local ethics committee, and the SAP.

7. Implementation of Analysis Plan

The data will be exported from REDCap to the statistical program STATA. An external statistician not involved in the study will assist with the statistical test.

STATA CODE

Poisson regression (example of code for fall rate):
poisson fallrate ib1.group, irr exposure(personyear)

Poisson regression with bootstrapping (example of code for fall rate):
poisson fallrate ib1.group, irr exposure(personyear) vce(bootstrap, reps(1000))

Poisson regression adjusting for age, sex, and fall history (example of code for fall rate):
poisson fallrate ib1.group age i.sex i.prev_faller, irr exposure(personyear)

Poisson regression with robust error variance (example of code for proportion of fallers):
glm faller ib1.group, fam(poisson) link(log) vce(robust) eform

Poisson regression with robust error variance adjusting for age, sex, and fall history (example of code for proportion of fallers):
glm faller ib1.group age i.sex i.prev_faller, fam(poisson) link(log) vce(robust) eform

Cox survival analysis (example of code for time to first fall):
stset firstfall, failure(faller==1)
stcox group

Cox survival analysis adjusted for age, sex, and fall history (example of code for time to first fall):

```
stset firstfall, failure(faller==1)  
stcox group age i.sex i.prev_faller
```

unpaired t-test (example of code for Global Patient Impression of Change (gpic)):

```
ttest gpic, by(group) unpaired
```

Unpaired two-sample Wilcoxon test (example of code for Global Patient Impression of Change):

```
ranksum gpic, by(group)
```

Fisher's exact (example of code for the proportion of fallers following slip perturbation at pre-training (t1)):

```
tabulate lab_slip_t1 group, exact
```

Linear mixed-effects model (example of code for single-task gait speed):

```
mixed gaitspeed_st group time || record_id:, var reml
```

In case of significant interaction effect, a posthoc analysis adjusted using the Bonferroni method is employed using the following code:

```
contrast rb1.time#group, mcompare(bonferroni)
```

Linear mixed-effects model adjusting for age, sex, and fall history (example of code for single-task gait speed):

```
mixed gaitspeed_st age i.sex i.prev_faller group##time || record_id:, var reml
```

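### The primary 12-month fall window opens at completion of session three, so randomised people who never complete it have no defined start date in an analysis called intention-to-treat

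*Combined protocol and SAP*

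**What the plan says.** Four parts of the combined protocol and SAP bear on when a participant's primary follow-up begins.

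- **Window (2.4.1):** "The primary endpoint will be the fall rate 12 months after completion of the third training session".
- **Randomisation (3.2):** "After the pre-training tests, participants will be randomly allocated to either the PBT or treadmill walking group". Allocation therefore precedes every training session.
- **Analysis sets (section 6, opening paragraph):** "All statistical tests will be performed using an intention-to-treat approach". In addition, "a per-protocol analysis will also be performed, including only participants who complete 75% or more of the training sessions".
- **Missing data (5.1):** fall rates are not imputed and days of follow-up enter as an offset. "For participants who do not return any fall calendars 0 falls and 0 person-years will be registered".

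The other places where a start date might stand do not supply one. Section 2.4.2 says "The secondary fall outcomes will be collected using the fall calendars for 12 months", which gives a length only, and Table 1 does the same. The primary model in the Stata code, "poisson fallrate ib1.group, irr exposure(personyear", takes person-years as already derived. The survival code for time to first fall sets no origin. Section 2.1 describes a four-session intervention and words the hypothesis in terms of the year after the intervention, which is not obviously the same window as the one in 2.4.1.

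**The concern.** Under intention-to-treat, everyone randomised should be able to contribute to the primary comparison from a time that the plan defines for them. Here the clock starts at a milestone that some randomised people may never reach. For them, the plan states neither whether they count nor from when, so someone must decide after the fact.

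If they are left out, the primary comparison is conditioned on attendance after randomisation. Attendance could differ by arm, because one arm receives repeated slips and trips and the other walks on a treadmill without perturbations. If early stoppers also differ in fall risk, the rate ratio would be biased, in a direction that cannot be known in advance. The gap matters in practice for people who stop training early but would still return fall calendars.

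**Working it through.** **1. Do the existing rules fill the gap?**

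- The follow-up offset adjusts for the length of follow-up. Length cannot be computed without a start date.
- The zero-person-years rule depends on returning no calendars, not on attendance. A person with zero person-years adds nothing to the Poisson likelihood, so the rule starts no clock. An early stopper who does return calendars is not covered.
- The intention-to-treat statement says who should be analysed, but not from when.

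**2. How does the window relate to the per-protocol set?** The per-protocol threshold is 75% of four sessions: 0.75 × 4 = 3 sessions. If the third session means the third one completed, the people with a defined window are exactly the per-protocol set. If it means the third scheduled visit, the two sets overlap but differ: someone attending visits 1, 2 and 4 would be per-protocol without a start date. The plan does not say which is meant.

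**3. What could leaving these people out do?** The documents give no attendance figures, so every input here except the 0.85, the 70 and the 20% used further down is an assumption. Suppose there is no true effect and the true mean fall rate is the same in both arms. Let s_p and s_c be the shares in PBT and control who do not complete session three, and m their fall rate relative to the rest. If all of them are left out:

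IRR = (1 + s_c(m − 1)) / (1 + s_p(m − 1))

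| s_p | s_c | m = 2 | m = 1 | m = 0.5 |
|---|---|---|---|---|
| 10% (7 of 70) | 0 | 1/1.10 = 0.91 | 1.00 | 1/0.95 = 1.05 |
| 10% | 5% | 1.05/1.10 = 0.95 | 1.00 | 0.975/0.95 = 1.03 |
| 10% | 10% | 1.00 | 1.00 | 1.00 |
| 0 | 10% | 1.10 | 1.00 | 0.95 |

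A more extreme assumption, 20% lost from PBT only at three times the rate, gives 1/(1 + 0.20 × 2) = 0.71.

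**4. How large is that against sampling error?** Take 56 people analysed per arm (70 less the planned 20% dropout, section 3.1), one year each, with 0.85 taken as the control rate. For the 0.91 case the expected falls are 56 × 0.85 = 47.6 and 47.6/1.10 = 43.3. The standard error of the log IRR is √(1/47.6 + 1/43.3) = 0.21. The shift is |ln(1/1.10)| = 0.095, or 0.095/0.21 = 0.45 standard errors, which moves the two-sided type I error from 5% to about 7.4%. For the 10%/5% case with m = 2 it is about 5.6%. Overdispersion would make the shift smaller relative to the standard error.

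**5. How much does collecting calendars recover?** Let r be the share of the early stoppers' follow-up that is recovered. Each arm's rate is then multiplied by ((1 − s) + s·r·m) / ((1 − s) + s·r), relative to its completers. For 10% in PBT only and m = 2:

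- r = 0: 1/1.10 = 0.91
- r = 0.5: (1.00/0.95)/1.10 = 0.96
- r = 0.8: (1.06/0.98)/1.10 = 0.98
- r = 1: 1.00

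A written start date therefore helps only as far as calendars are actually obtained.

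**The case against.** The strongest reply is that the intent is plain. Intention-to-treat is applied to all tests, a separate attendance-restricted analysis is planned, and the only stated ground for contributing no person-time is returning no calendars. A per-protocol analysis would be pointless if the primary window already admitted only people with three sessions. This stands as evidence of intent, but it does not supply a date.

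Second, the comparator is time-matched treadmill walking (2.1), so the same milestone applies in both arms. If it is reached equally often and selects similarly, the illustration gives 1.00. This limits the risk without removing it, because tolerance of perturbations could still differ by arm.

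Third, every figure for bias is assumed, and the 0.91 needs loss in one arm only, at double the fall rate, with all of those people left out. The planned effect is a 50% reduction. This is correct, and it is why the point rests on the undefined rule and not on a number.

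Fourth, opening the window after training is a defensible choice when the hypothesis concerns falls after the intervention. That is accepted; the start used for people who complete session three need not change.

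A reader might infer that the plan excludes non-completers, or that its primary analysis is a per-protocol analysis under another name. The documents do not support this: no passage excludes them, and the match with the per-protocol set depends on an unstated meaning of the third session. Nor do they support the inference that the result will favour PBT, since the illustration runs on both sides of 1.

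**Conclusion.** The point holds as a gap in the definition of the primary endpoint that, applied literally, contradicts the intention-to-treat statement. It is more than a missing detail, because the rule as written gives a window only to people who reached an attendance milestone after randomisation.

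Its size is unknown. The documents give neither the number expected to stop before session three, nor their fall risk, nor the session dates. The illustrated ratios around 1 rest entirely on assumed shares and relative fall rates, and the bias is nil if loss is equal in both arms and unrelated to fall risk. The plan should be corrected before analysis, but nothing in the documents shows that the primary comparison is already compromised.

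**What to change.** - **2.4.1:** Keep completion of session three as the start for those who complete it. For every other randomised participant, start the window on the date session three was scheduled, whatever their attendance. State how that date is set if it was never booked, and whether the third session means the third completed or the third scheduled.
- **5.1 and section 6:** Issue and collect calendars from all randomised participants, and include everyone with follow-up in the primary Poisson model.
- **Sensitivity analysis:** Use one attendance-independent time zero for all: the planned session-three date, or randomisation where calendars cover that period.
- **Reporting:** Give by arm the number who did not complete session three. If calendars were issued only after completion, say so, give the affected numbers by arm, and do not describe the primary analysis as full intention-to-treat.
- **2.1:** Reconcile the year after the intervention with the window in 2.4.1.

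The cost is a few sentences and a few more calendars; the planned 70 per group does not change. The nominal start date is somewhat arbitrary for non-completers. Some data may also be beyond recovery: the SAP says of the analyses by fall history, "These sensitivity analyses were planned after data collection began", so the trial was already under way when that part of the plan was made. For people who had already stopped without calendars, the change may bring only clear reporting.

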2.4.2. Secondary Endpoints

Secondary outcomes and their endpoints are outlined in table 1 and 2. The secondary fall outcomes will be collected using the fall calendars for 12 months. The fall-related risk factor outcomes will be collected at the pre- and post-training test and the 26- and 52-week follow-up.

3. Study Design

This study is designed as an assessor-blinded, randomised, parallel-group (1:1 ratio), controlled trial

3.1. Sample Size

The sample size calculation was conducted in G*power (version 3.1.9.4, University of Kiel, Kiel, German) using a Poisson regression model. The calculation was made with certain assumptions (80% power, 5% significance level, 50% difference in fall rate (favouring the PBT), and 20% dropout rate) and an expected average fall rate of 0.85.[18–21] This resulted in an estimated required sample size of 70 participants in each group.

3.2. Randomisation and Blinding

After the pre-training tests, participants will be randomly allocated to either the PBT or treadmill walking group using a permuted block randomisation module in REDCap to ensure similar group sizes (Research Electronic Data Capture; version 9.5.6). Random block sizes (two, four, six, or eight) will ensure that allocation concealment is maintained. The allocation sequence will be generated by a research staff member not involved in enrolling or assigning participants to groups.

4. Study Population

4.1. Subject Disposition

One hundred forty community-dwelling older adults (70 in each group) living in and around Aalborg will be recruited via informal presentations about the trial, local and national newspapers, radio and television spots, flyer hand-outs, and snowball sampling. Participants are eligible if they are 1) ≥ 65 years old, 2) community-dwelling, and 3) able to walk without a walking aid. Participants will be excluded if they 1) have any of the following self-reported conditions: orthopaedic surgery within the past 12 months, osteoporosis or history of osteoporosis-related fractures (low-impact hip, spine, and wrist fracture), or progressive neurological disease (e.g., Parkinson), 2) have an unstable medical condition that would prevent safe participation, 3) have

a severe cognitive impairment (a score <8 in The Short Orientation-Memory-Concentration Test)[22], or 4) are currently participating in another fall prevention trial.

5. Data handling

All data will be collected and managed using the secure, web-based software platform REDCap hosted in The Region of Northern Denmark.[23,24] The data collection forms in REDCap ensure strong data integrity by applying functions that check for mandatory information, data ranges, and alerts whenever data violates specific limits.[24] To ensure data quality, all outcomes will be visually inspected for implausible values before the dataset is locked. Missing and out-of-range data in REDCap will also be assessed compared to original data files (paper documents for questionnaires and FysioMeter software for balance and reaction time) and corrected in cases of discrepancies. REDCap also logs every record activity, which will be used to monitor data validity.

